	sensation of vertigo and dizziness as change from baseline
	to month $2\pm 1$ assessed by the Dizziness Handicap
	Inventory (DHI; total).
Secondary Endpoints	• Effect of Vertigoheel ® on QoL as change from baseline to
	month $2\pm 1$ assessed by EQ-5D-5L.
	• Effect of Vertigoheel ® on total sway path as change from
	baseline to month $2\pm 1$ assessed by static posturography.
	• In FD effect of Vertigoheel ® on psychiatric symptoms as
	change from baseline to month $2\pm 1$ assessed by Patient
	Health Ouestionnaire Mood Scale (PHO-9) and
	Generalized Anxiety Disorder Screener (GAD-7)
	• In BVP effect of Vertigoheel ® on vestibular function as
	change from baseline to month 2+1 assessed by video
	head impulse test (vHIT) and/or caloric testing
	• Adverse events (AFs)
	
 
Other observations related to safety (physical examination)
 

	and vital signs)
Study Design	Non-interventional observational prospective monocentric
Study Design	study
Study Population	It is planned to include 20 patients with BVP and 40 patients
	with ED who are going to start Vertigoheel ® treatment
	according to clinical practice at the study conter
	The desision of treatment is up to the physician's discretion
	The decision of treatment is up to the physician's discretion
Inclusion / Evolusion	and is to be made independent of this study.
Criteria	Following documentation criteria should be fulfilled
Cintoina	• BVP (according to the diagnostic criteria of the Bárány
	Society) or FD (according to the diagnostic criteria of the
	Bárány Society).
	• Symptoms for > 3 months of moderate to severe intensity
	according to the DHI [0 (minimum score) -100 (maximum
	score)] of 30 to 90 points.
	• $\geq 18 - 80$ years of age.
	• Legally competent male or female outpatient.
	Signed informed consent.
	• Not pregnant (as proven by negative pregnancy test in
	case of woman of childbearing potential before first
	study drug administration) or breast-feeding.
	Patients with the following conditions are excluded from the
	documentation in this NIS
	• Ongoing (within the last two months) or recently started
	Vertigoheel ® treatment.
	• Debilitating acute or chronic illness (e.g. psychiatric
1	
	illnesses).

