## 4.2 POSTUROGRAPHY

Posturography is used to assess regulation of stance and gait. A platform is used to measure body sway, which can exist in healthy subjects because of inherent physiological postural instability and which is increased in vestibular disorders.

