## 9 DATA MANAGEMENT

#### **Data Source**

Data for this study will be obtained from various sources, including treating physicians and source documentation such as questionnaires and examination methods for vertigo. The investigator will record relevant medical data, participation in the study and the occurrence of adverse events. Treatment related data during visits that take place in routine practice will be collected as source data in the respective patient's records. The outcomes will be captured from validated examination methods for vertigo (i.e. posturography, vHIT, caloric testing). The investigator must keep supportive original source documentation for all patient-related data.

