The purpose of this statistical analysis plan (SAP) is to ensure that the data listings, summary tables, and figures which will be produced, and the statistical methodologies that will be used, are complete and appropriate to allow valid conclusions regarding the trial objectives.

The SAP outlines the following:

- Study objectives
- Study design
- Variables analyzed and analysis sets
- Statistical methods regarding trial drug exposure, effectiveness analysis, concomitant medications, adverse events handling, laboratory data, vital signs and physical examinations
- Tables, Listings, Figures (TLFs)
- This SAP is based on the Observational Plan, Final Version 1, dated 28-JUN-2021 and pCRF Final Version 1, dated 23-NOV-2021.

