2.2 Secondary Objectives

- To evaluate the change from baseline in QoL after 2±1 month of routine Vertigoheel® treatment measured by questionnaires
- To evaluate the change from baseline in postural imbalance after 2±1 month of routine Vertigoheel® treatment for patients suffering from FD and BVP
- To evaluate the change from baseline in psychiatric symptoms after 2±1 month of routine Vertigoheel® treatment for patients suffering from FD measured by questionnaires

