5.3.2 Posturography

Posturography is used to assess regulation of stance and gait.

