5.4 Data Analysis

SAS or R software, or an equivalent software package will be used for statistical analysis.

Descriptive statistics will be provided for all parameters. The statistics will be appropriate for the type of data:

- For continuous and count variables, statistics will include the number of observations, mean, standard deviation, median, minimum, maximum, and two-sided 95% confidence interval (CI).

- For categorical variables, the descriptive statistics will include the count and percent of observations in each category along with its Clopper-Pearson two-sided 95% CI. The denominator for the percentage calculation will be based on the number of patients in the analysis population.

This is a non-interventional, observational study, therefore only CI are calculated. All endpoints will be analyzed by the appropriate type of descriptive statistic(s) as described above.

All variables will be analyzed in an exploratory manner. No formal statistical hypothesis testing will be performed.

Missing values will not be imputed.

The following subgroups will be defined:

- Patients with FD
- Patients with BVP

It is planned to include 20 patients with BVP and 40 patients with FD.

No further subgroups will be defined.

Shift tables for physical examination, DHI, Posturography, and vHIT will display the number and percentage of patients per baseline value category vs. the worst value category post-baseline

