Appendix 1: Tables, Listings, Figures

Item No.	Title	Population	Content Description
14.1	Disposition, Baseline Characteristics, Medication and Further Analyses		
14.1.1	Patient disposition	All	Descriptive statistics on patients screened, failed screening, treated
14.1.2	Early termination	All	Descriptive statistics for early termination yes/no
14.1.3	Number of patients in each analysis population	All	Descriptive statistics for number and percentage of patients and reason for exclusion
14.1.4	Duration of study	All	Date of first patient in and last patient out of all patients
14.1.5	Duration of observation per patient	SP	Difference of Date of patient in and patient out per patient
14.1.6	Demographics and other baseline characteristics	ITT	Descriptive statistics of age, , height, weight, pregnancy test
14.1.7.1	Vital signs	ITT	Descriptive statistics of heart rate and blood pressure, at Screening Visit and 2±1 month after baseline
14.1.7.2	Physical examination	ITT	Descriptive statistics (normal, abnormal, ncs (not clinically significant), cs (clinically significant)), at Screening Visit and 2±1 month after baseline (shift table)
14.1.8.1	Primary diagnosis	ITT	Descriptive statistics of 
 - FD yes/no (derived from tick box 'NA' for caloric (BVP)) - BVP yes/no (derived from tick box 'NA' for GAD-7 (FD))
14.1.8.2	Medical history - Abuse history	ITT	Descriptive statistics of alcohol and drug consumption, smoking status
14.1.9.1	Treatment with Vertigoheel	SP	Descriptive statistics for 
 - Duration of treatment (date start of study – date start of Vertigoheel treatment - change of Vertigoheel dose yes/no
14.1.9.2	Prior medication	SP	Descriptive statistics for prior medication yes/no
14.1.9.2	Concomitant medication	SP	Descriptive statistics for change of concomitant medication yes/no
14.1.9.3	Product complaints	SP	Descriptive statistics for product complaint yes/no

14.2	Patient Reported Outcomes (Effectiveness)		
14.2.1	Primary Endpoint		
14.2.1	Dizziness Handicap Inventory	ITT	Descriptive statistics at Screening Visit and 2±1 month after baseline (yes, sometimes, no), and change from baseline to 2 months (shift table)
14.2.2	Secondary Endpoints		
14.2.2.1	Posturography	ITT	Descriptive statistics at Screening Visit and 2±1 month after baseline (normal, neuritis vestibularis, PPV), and change from baseline to 2±1 month after baseline (shift table)

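### The SAP tabulates posturography only as categories, so no listed table carries the protocol's secondary endpoint, change in total sway path with a 95% CI

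*SAP*

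**What the plan says.** **Protocol.** The Secondary Endpoints entry of the Observational Plan Summary sets the effect of the product "on total sway path as change from" baseline to month 2±1, assessed by static posturography. Section 4.2 describes a quantitative measurement: "A platform is used to measure body sway". Section 2.2 words the matching objective only as postural imbalance, in FD and BVP.

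**SAP.** Section 2.2 retains that objective: "To evaluate the change from baseline in postural imbalance after 2±1 month of routine" treatment, again for both indications. Section 5.3.2, which should define the endpoint, consists of one sentence: "Posturography is used to assess regulation of stance and gait". Section 5.4 then assigns the analysis: "Shift tables for physical examination, DHI, Posturography, and vHIT will display the number and percentage of patients per baseline value category", set against the worst category after baseline. In Appendix 1, Table 14.2.2.1 gives the content for the ITT population at both visits as "normal, neuritis vestibularis, PPV), and change from baseline to 2±1 month after baseline (shift table". No other listed table covers posturography.

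**The concern.** Total sway path is an amount, and its change is a difference between two amounts. The three entries in Table 14.2.2.1 are labels. Tabulating labels answers a different question from the one the protocol set, and the SAP neither announces nor explains the substitution.

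If the table list is programmed as written, the report will hold no estimate of the size or direction of change in sway path, which is the only variable the protocol names for its postural-imbalance objective. A patient whose sway path changes while the label stays the same would be counted as unchanged. The study is descriptive and uncontrolled, so its estimates and confidence intervals are its whole result. An endpoint without an estimate is therefore an endpoint without a result.

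**Working it through.** This is mainly a comparison of texts. The arithmetic shows only what the listed output can and cannot deliver.

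**1. Is sway path named anywhere in the SAP?** The places that mention posturography or its objective are 2.2, the flow chart in section 4, 5.3.2, 5.4 and Table 14.2.2.1. None names sway path, a unit, a stance condition or a score. Section 14.2 has seven effectiveness tables: DHI, posturography, EQ-5D-5L, PHQ-9, GAD-7, vHIT and caloric testing. None of the seven names sway path. The count that matters is the one posturography table, and it does not.

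**2. Is that just the style of the appendix?** No. Other rows say what is summarised: a total score for PHQ-9 and for GAD-7, each parameter for caloric testing, each question for EQ-5D-5L. The posturography row also says what is summarised, and it is categories.

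**3. Can the categories yield the endpoint?**
- SAP 5.6.2 defines change as the post-baseline value minus the baseline value. That subtraction has no meaning for labels.
- SAP 5.4 compares baseline with the worst category after baseline, but the SAP never ranks neuritis vestibularis against PPV. A move between these two has no stated direction.
- Under 5.4 the percentages receive Clopper-Pearson intervals. For an observed 50%, these run from 27.2% to 72.8% at n = 20 and from 33.8% to 66.2% at n = 40. They are intervals for a proportion and say nothing about a mean change.

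**4. Does the plan's precision figure help?** SAP 5.1 gives a 95% CI half-width of 0.351 at n = 20 with SD 0.8. It reproduces with the normal quantile: 1.96 × 0.8 / √20 = 0.351. The protocol synopsis ties the SD of 0.8 to a vertigo-attack intensity score in an earlier trial, so it is not a sway-path SD. No half-width in sway units can be derived from the documents.

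**5. What would a sway-path analysis give?** The half-width can be stated in units of the unknown SD of the change, as t(0.975, n − 1) / √n:

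| Group | n | Half-width (SD units) |
|---|---|---|
| BVP, planned | 20 | 0.468 |
| BVP, 10% loss | 18 | 0.497 |
| FD, planned | 40 | 0.320 |
| FD, 10% loss | 36 | 0.338 |
| FD, 20% loss | 32 | 0.361 |
| FD, 30% loss | 28 | 0.388 |

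The 10% loss is in SAP 5.1. The 20% to 30% for FD is in the protocol synopsis.

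**6. How much data is involved?** 20 + 40 = 60 planned patients, and 60 × 2 visits = 120 scheduled examinations before any loss to follow-up.

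**The case against.** The strongest reply is that the method is already in the SAP. Section 5.4 promises descriptive statistics for every parameter and every endpoint, with mean, SD and a two-sided 95% CI for continuous variables. Appendix 1 only names content. None of its section 14.2 rows mentions a mean or a CI, so the absence of a CI does not single out posturography. This stands in part: the gap lies in the named variable and the table list, not in the general method. But the general rule reaches sway path only if it is recorded as a number. The SAP rests on the Observational Plan "and pCRF Final Version 1, dated 23-NOV-2021", and that form is not among the documents. Whether a number is captured cannot be checked.

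Second, the protocol shares the blame. Sway path appears only in its synopsis, and its body gives no variable, unit or test condition. The SAP also cites a plan dated 28-JUN-2021, while pages of the supplied plan carry 15JULY2021 and 27MAY2021. This is true and should be tidied up. All three are labelled Version 1, however, and the SAP keeps the postural-imbalance objective, so the mismatch remains.

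Third, the study is descriptive, SAP 5.3 declines to separate primary from secondary endpoints, and assessments follow routine practice. That limits the stakes. It does not remove the endpoint, and Appendix 1 itself files posturography under secondary endpoints.

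**Conclusion.** The concern holds. The supplied SAP names no sway-path variable, lists posturography only as categories, and has no table for change in total sway path with its 95% CI. That much is certain from the text. That the endpoint would go unreported is conditional: it follows if the table list is programmed as written, or if the case report form holds no numeric value. The loss of information cannot be sized, because the documents give no mean or SD for sway path and do not say how the three categories are assigned. This is one secondary endpoint in a descriptive study and it can be repaired, so the change should be made, but the gap does not undermine the study as a whole.

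**What to change.** In SAP 5.3.2 and Table 14.2.2.1, name total sway path as a continuous variable, with its unit and test condition. Summarise it at the Screening Visit and Visit 1. Report absolute change as defined in 5.6.2 with a two-sided 95% CI, separately for the FD and BVP subgroups that 5.4 already defines. Keep the category frequencies and shift table as supportive output. If sway path was not captured and cannot be recovered, state in the SAP that this protocol endpoint is not evaluated, and why.

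If the values are already in the database, the cost is SAP wording and one table. If the form holds only categories, two values per patient must be transcribed from source: up to 60 × 2 = 120 values, plus any for replaced patients. The protocol's Data Source section supports this: "The investigator must keep supportive original source documentation for all patient-related data". It works only where those records contain the measurement. Protocol section 4 leaves assessments to routine practice, so test conditions may differ between visits and should be recorded alongside each value.

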### 2.2 SECONDARY OBJECTIVES

- To evaluate the change from baseline in QoL after 2±1 months of routine Vertigoheel® treatment measured by questionnaires.
- To evaluate the change from baseline in postural imbalance after 2±1 months of routine Vertigoheel® treatment for patients suffering from FD and BVP.
- To evaluate the change from baseline in psychiatric symptoms after 2±1 months of routine Vertigoheel® treatment for patients suffering from FD measured by questionnaires.

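### SAP item 14.2.2.1 reports posturography under three undefined, unordered labels, none of which evidently fits an abnormal bilateral vestibulopathy recording

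*SAP*

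**What the plan says.** The secondary objective in SAP 2.2 reads "To evaluate the change from baseline in postural imbalance after 2±1 month of routine Vertigoheel® treatment for patients suffering from FD and BVP". Protocol 2.2 sets the same objective for both diseases. The Observational Plan Summary in the protocol makes it a measurable endpoint: the effect "on total sway path as change from" baseline to month 2±1, "assessed by static posturography".

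The SAP does not mention sway path. Section 5.3.2 describes posturography in one sentence, with no variable, unit or scoring rule. Appendix 1, item 14.2.2.1, lists the output on the ITT population under the levels "normal, neuritis vestibularis, PPV", with change from baseline given as a shift table. SAP 5.4 includes posturography among the shift tables that set "baseline value category vs. the worst value category post-baseline".

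On numbers, SAP 5.4 states: "It is planned to include 20 patients with BVP and 40 patients with FD".

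**The concern.** The objective asks whether imbalance changed in each of two diseases. The planned table answers with labels that look like diagnostic patterns. One of them, neuritis vestibularis, is not a study diagnosis. Another, PPV, is missing from the protocol's abbreviation list. The only matching phrase in the documents is phobic postural vertigo, in the title of a cited review of functional dizziness. Nothing refers to BVP.

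Two things are at stake. First, whoever codes an abnormal BVP recording has no instruction: it could go under another condition's label, be called normal, or be left blank, and the choice could differ between patients or visits. Second, the table shows direction only for moves to or from normal. A move between the two abnormal labels is neither better nor worse, in FD as much as in BVP. A programmer following the SAP as written would deliver the table, and it would not answer the objective.

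**Working it through.** No figure in the plan describes this table, so the check is mainly a comparison of texts, followed by a count.

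**1. Are BVP patients meant to be in the table?** Yes. The population for 14.2.2.1 is ITT without restriction. PHQ-9 and GAD-7 (14.2.2.3, 14.2.2.4) are limited to FD, and vHIT and caloric testing (14.2.2.5, 14.2.2.6) to BVP. Both flow charts mark those four tests by disease and schedule posturography for everyone.

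**2. Is there a level for an abnormal BVP recording?** None that is evident. The listed levels are normal and two others, neither naming BVP, with no level for other, pathologic or not done. In the same appendix, vHIT has a disease-neutral scheme: not done, normal, pathologic.

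**3. Are abnormal BVP recordings likely?** The documents suggest so. Protocol 1.1 names postural imbalance as a leading symptom of BVP, and protocol 4.2 says body sway is increased in vestibular disorders. Neither gives a proportion.

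**4. Can the shift rule in SAP 5.4 be applied?** Choosing a worst category requires an order. None is stated, and none is evident between neuritis vestibularis and PPV.

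**5. Does another SAP output cover the objective?** Not by name. SAP 5.4 promises n, mean, SD, median, range and 95% CI for continuous variables in general, but no section or table lists sway path as a variable.

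**6. How many patients are exposed?** Inputs: 20 BVP and 40 FD planned (SAP 5.4); 10% loss to follow-up (SAP 5.1).

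- As planned: 20 / (20 + 40) = 20/60 = 33.3%.
- After 10% loss in both groups: BVP 20 × 0.9 = 18; FD 40 × 0.9 = 36; 18 / (18 + 36) = 18/54 = 33.3%.

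Both are upper bounds. They count every BVP patient, whereas only those with an abnormal recording lack a fitting level.

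**The case against.** The strongest reply is that the labels may be sway-pattern classes produced by the recording system and not diagnoses, so that a BVP recording could be assigned by a rule kept elsewhere. The SAP rests on a paper CRF that is not among the documents and may hold an extra field or a coding instruction. This stands in part: the documents show that the mapping is unspecified, not that it is impossible.

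A reader might infer that none of the 20 BVP patients can be validly scored. The documents do not support that, because a BVP patient with a normal recording fits the normal level.

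A reader might also put the share at 36% to 39%, using the 20% to 30% FD loss in the protocol's summary: 18 / (18 + 32) = 36% and 18 / (18 + 28) = 39%. Protocol section 8 and SAP 5.1 give a single 10%, so that range rests on one side of a conflict in the plan. Nor does it follow that the category percentages can total at most 40/60 = 67%. That assumes every BVP recording, normal ones included, is left blank, and it uses planned enrolment although ITT requires a post-baseline measurement.

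On the worst-category rule, one visit is scheduled after baseline. With a single later recording the rule simply returns that recording. The missing order matters for selection only when an unscheduled visit, which protocol 6.6 allows, adds another. It matters for interpretation in every case.

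Finally, this is a secondary endpoint in a descriptive study without hypothesis tests, and no improvement rule uses the labels. That limits the severity, but the stated objective still has no output that addresses it.

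**Conclusion.** The concern holds in this form: item 14.2.2.1 applies undefined and unordered labels to both diseases, offers no evident level for an abnormal BVP recording, and sits under a shift rule that presupposes an order the labels lack. As written, the table cannot answer the postural-imbalance objective. For BVP the gap is one of coding as well as interpretation; for FD it is one of interpretation.

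The coding gap reaches at most 33% of patients (20 of 60 planned, 18 of 54 after 10% loss). The actual number depends on how many BVP recordings are abnormal, which the documents do not give. The conclusion assumes that no definition or extra level exists in the unseen CRF; if one does, the SAP should cite it. The change should be made before the tables are programmed, but it does not threaten the primary endpoint.

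**What to change.** - **Item 14.2.2.1 and SAP 5.3.2:** make the posturography result the protocol endpoint, change in total sway path from baseline to Visit 1. State the unit and test condition, and report mean change with 95% CI separately for FD and BVP, which SAP 5.4 already defines as subgroups.
- **Categorical table, if kept:** either restrict it to FD and define the three labels, or use not done, normal and pathologic for both groups.
- **SAP 5.4:** remove posturography from the worst-category rule unless an order is defined.

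The first and third changes belong together with any restriction to FD. Restricting the table without naming sway path would leave BVP with no specified posturography output.

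Cost: SAP wording only, provided the CRF captured sway path as the protocol endpoint implies. If it did not, the values would have to come from source recordings, where these hold them, or the gap be reported as a limitation. The downside is that BVP would have no summary by diagnostic pattern.

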## LIST OF ABBREVIATIONS

AE	Adverse event
AMG	"Arzneimittelgesetz" (German Medicinal Act)
AWMF	"Arbeitsgemeinschaft der Wissenschaftlichen Medizinischen
	Fachgesellschaften" (Working group of scientific medicine societies)
BfArM	"Bundesinstitut für Arzneimittel und Medizinprodukte"
	(German federal institute for drugs and medical devices)
BL	Baseline
BVP	Bilateral vestibulopathy
CI	Confidence interval
СМ	Concomitant medication
CRO	Clinical research organization
CSR	Clinical study report
DBL	Database lock
DHI	Dizziness handicap inventory
eCRF	Electronic case report form
EDC	Electronic data capture
EFPIA	European federation of pharmaceutical industries and associations
EQ-5D-5L	European quality 5 dimensions 5 level
FD	Functional dizziness
FPI	First patient in
GAD-7	Generalized anxiety disorder scale
GCP	Good clinical practice
HIT	Head impulse test
ITT	Intention to treat
KBV	"Kassenärztliche Bundesvereinigung" (National association of statutory health
	insurance physicians
LPO	Last patient out
NIS	Non-interventional study
MH	Medical history
PHQ-9	Patient health questionnaire
РР	Per protocol
PRO	Patient Reported outcome
QoL	Quality of life
SAE	Serious adverse event
SmPC	Summary of product characteristics
SOP	Standard operational procedure
V	Visit
vfa	"Verband der forschenden Pharmaunternehmen" (Federation of pharmaceutical
	industries doing research)
vHIT	Video head impulse test
VOR	Vestibulo-ocular reflex

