## 4.3 EQ-5D-5L

The EQ-5D-5L is a self-administered questionnaire for evaluating QoL introduced in 2009 [EuroQol Group, 2017]. It is a multiple-choice questionnaire and a visual analogue scale that takes only few minutes to complete and is a standardized instrument for measuring generic health status. It has been widely used in population health surveys, clinical studies, economic evaluation and in routine outcome measurement in the delivery of operational healthcare.

In patients suffering from FD due to increased rates of psychiatric comorbidities:

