5.3.3 EQ-5D-5L

The EQ-5D-5L is a self-administered questionnaire for evaluating QoL.

In patients suffering from FD due to increased rates of psychiatric comorbidities:

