14.2.2.2	Quality of Live (EQ-5D-5L)	ITT	Descriptive statistics per question, at Screening Visit and Visit 1, and change from baseline to 2 months
14.2.2.3	Patient Health Questionnaire depression module (PHQ-9)	ITT In patients with FD	Descriptive statistics for total score, at Screening Visit and Visit 1, and change from baseline to 2 months
14.2.2.4	Generalized anxiety disorder scale (GAD-7)	ITT In patients with FD	Descriptive statistics for total score, at Screening Visit and Visit 1, and change from baseline to 2 months
14.2.2.5	Video head impulse test (vHIT)	ITT In patients with BVP	Descriptive statistics at Screening Visit and Visit 1 (not done, normal, pathologic), and change from baseline to 2 months (shift table)
14.2.2.6	Caloric testing	ITT In patients with BVP	Descriptive statistics per parameter, at Screening Visit and Visit 1, and change from baseline to 2 months

14.3	Safety Analyses		
14.3.1	Adverse Events		
14.3.1.1	Overview of adverse events	SP	Number and percentage of patients with adverse events (yes/no), intensity (mild, moderate, severe), causality (related, not related, unknown)

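### EQ-5D-5L is to be summarised question by question with no overall measure named, so the secondary quality-of-life objective has no single pre-specified estimate

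*SAP*

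**What the plan says.** SAP 2.2 states the objective as one quantity: "To evaluate the change from baseline in QoL after 2±1 month of routine Vertigoheel® treatment measured by questionnaires". Protocol 2.2 has the same objective. The protocol's Observational Plan Summary makes the endpoint the change in quality of life assessed by EQ-5D-5L, without naming a score.

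Protocol 4.3 describes the instrument: "It is a multiple-choice questionnaire and a visual analogue scale". SAP 5.3.3 is shorter and leaves the scale out: "The EQ-5D-5L is a self-administered questionnaire for evaluating QoL".

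The analysis is set only in SAP Appendix 1, Table 14.2.2.2: "Descriptive statistics per question, at Screening Visit and Visit 1, and change from baseline to 2 months". The two rows below it, for PHQ-9 and GAD-7, ask for the same statistics on the total score.

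**The concern.** The objective asks about quality of life as a whole, while the table delivers separate answers to separate questions. Nothing says which of them, or what combination, is the quality-of-life result. If one dimension improves and another worsens, the plan has no rule for what to conclude.

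The item changes are also hard to interpret. Each item is a five-level ordinal response, and a difference between level codes has no natural unit.

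What is at stake is how the report is worded. Quality of life is in the study title and in the rationale aimed at health insurers, so a reader will look for one statement on it. With no measure named in advance, the authors choose which dimension to stress after seeing the data.

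**Working it through.** The plan gives no figure for EQ-5D-5L. Its only precision figure, 0.351 at n = 20, reproduces as 1.96 × 0.8 / √20 = 0.351, but it is not specific to this instrument and the point does not depend on it. The check is a comparison of texts and a count.

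**Is an overall measure named anywhere?**

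| Place | What it specifies for EQ-5D-5L |
|---|---|
| Protocol, Observational Plan Summary | Change assessed by the instrument; no score |
| Protocol 4.3 | Multiple-choice items and a VAS; no scoring rule |
| SAP 5.3.3 | A questionnaire; no VAS, index or value set |
| SAP 5.4 | Descriptive statistics for every parameter; no EQ-5D-5L summary |
| SAP Table 14.2.2.2 | Each question, at both visits and as change |
| SAP Tables 14.2.2.3 and 14.2.2.4 (PHQ-9, GAD-7), for contrast | Total score |

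No overall measure is named. The SAP does name a total score for the two neighbouring questionnaires.

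**How many results does the row produce?** The protocol's abbreviation list expands the name as "European quality 5 dimensions 5 level", which I take to mean five items with five levels each. SAP 5.4 defines two subgroups, FD and BVP.

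- VAS not counted as a question: 5 changes per group, 5 × 2 = 10 in all.
- VAS counted as a question: 6 per group, 6 × 2 = 12 in all.
- One named measure: 1 per group, 1 × 2 = 2 in all.

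**What does change mean for an item?** SAP 5.6.2 defines it only as the post-baseline value minus the baseline value. SAP 5.4 lists shift tables for physical examination, DHI, posturography and vHIT, but not for EQ-5D-5L, and the EQ-5D-5L row does not mention one. Two treatments remain possible.

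- Numeric: mean change in level codes. As an illustration with consecutive codes, a patient who moves one level down in one dimension and one level up in another has item changes of −1 and +1. The plan does not say whether quality of life improved, worsened or stayed the same.
- Categorical: counts, percentages and Clopper-Pearson intervals. That gives 5 × 5 = 25 percentages per visit per group, and subtraction does not define change for a category.

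The SAP does not say which applies. Neither gives an overall estimate.

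**The case against.** The study is descriptive, tests no hypothesis and may properly report individual items. Four arguments in the plan's favour deserve weight.

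- **The VAS may already be covered.** Reporting by question can be read to include it, and SAP 5.4 undertakes to summarise every parameter. This stands. A reader might infer that the objective goes unanswered, but the documents do not support that. The supportable statement is that no measure is designated as the result and that coverage of the VAS is unclear. Even if tabulated, it would be one of six unranked results.
- **Every question is to be reported.** A reader might infer that unfavourable dimensions could be left out. The table commits to all of them at both visits and as change, so the risk is selective emphasis, not selective reporting.
- **There is no error rate to inflate.** A reader might compute 1 − 0.95⁵ = 22.6% as the chance that at least one of five intervals excludes zero when nothing has changed. That does not measure this problem. No decision in the plan rests on an interval excluding zero, and the figure assumes independent items, whereas items of one questionnaire are likely to be positively correlated. It is not an upper bound either: without the independence assumption the bound is 5 × 5% = 25%.
- **Items could be handled as categories.** SAP 5.4 asks for statistics suited to the type of data, which would avoid means of ordinal codes. This is a fair reading, but the SAP does not state it, and the change would then need a shift table that is not listed.

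The absence of a named overall measure survives all four.

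**Conclusion.** The point holds as a minor one. Table 14.2.2.2 is the only EQ-5D-5L analysis specification. It names no overall quality-of-life measure and leaves the VAS unclear, so the secondary objective has no single pre-specified estimate. Its size is five or six unranked results per diagnosis group where one would answer the objective, plus an item-level change without a clear unit if level codes are subtracted.

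This assumes that the instrument's name gives its number of items and levels. It also takes the SAP as it stands: the CRF, which might show how the responses are recorded, is not among the documents. The DHI result and the safety analyses are unaffected.

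**What to change.** In SAP Table 14.2.2.2 and SAP 5.3.3, name one overall EQ-5D-5L measure as the quality-of-life result before database lock. Report its mean change from baseline with a 95% CI, separately for FD and BVP.

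The VAS score is the simplest choice because it needs no value set; first confirm that the CRF captures it. The index value can serve instead, or as a supportive measure, if the SAP names the value set. Report the five dimensions as supportive frequency or shift tables, which also settles how item-level change is shown.

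The cost is an edit to two places in the SAP and a small amount of extra analysis, plus the choice of a value set if the index is used. No new assessment is needed, since both flow charts already schedule EQ-5D-5L at baseline and at Visit 1.
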